## 1. ABSTRACT

Chinese Americans are one of the fastest growing immigrant groups in the US, who suffer disproportionately high type 2 diabetes (T2D) burden and have poorly controlled T2D. Given the high economic and societal burden of T2D and rapid population growth in Chinese Americans, there is an urgent need for research to develop effective interventions to address T2D burden in this population. Recent evidence suggests the importance of involving and empowering family members in diabetes intervention and calls for family intervention. A mobile health approach such as short message service (SMS) might be a promising way to deliver such family-oriented interventions to the target population given prior studies suggests that Chinese Americans often report challenges to attend in-person lifestyle counseling because of long working hours and lack of sick time from work. A SMS-based intervention provides the flexibility of allowing them to view the intervention at a time and place convenient to them. However, such intervention has not been developed for or tested in Chinese Americans with T2D. This study will serve as the first step to explore an alternative approach for managing T2D in this group. The goal of this pilot study is to examine the feasibility and acceptability of a family-oriented SMS intervention in 30 pairs of Chinese Americans with T2D and their family members. Participants will be randomized to one of 2 arms (n=15 pairs each): 1) wait-list control and 2) SMS intervention. Both groups will continue to receive standard of care treatment for their T2D. The SMS group will receive brief lifestyle counseling videos via SMS links. At the end of the study, the wait-list control group will be provided the opportunity to receive the counseling videos. Measurements will be obtained at baseline, 3, and 6 months. The primary outcome is feasibility and acceptability, and secondary outcomes include HbA1c, self-efficacy, and diabetes self-management behaviors. Findings from this pilot study will inform a larger full-scale R01 efficacy trial of the SMS intervention, and ultimately, an implementation study in the real-world setting. This project can serve as a program model for other chronic disease interventions in Chinese Americans that require lifestyle modification (e.g., prediabetes, hypertension), or for disparities research in other high-risk immigrant populations (e.g., South Asians, Hispanic Americans).

## 2. PURPOSE OF THE STUDY AND BACKGROUND

### 2.1 *Background*

Chinese Americans are one of the fastest growing immigrant groups in the United States. Multiple studies show that, compared to non-Hispanic whites, Chinese Americans suffer disproportionately higher rates of type 2 diabetes (T2D), have poorer self-management and glycemic control, and are at elevated risk of developing renal complications. Lack of culturally and linguistically sensitive healthcare providers and programs are the most commonly cited reasons for disparities in T2D care and health outcomes in Chinese Americans. High rates of limited English proficiency, poor access to healthcare and patient-provider communication barriers have played a critical role in prevention and management of T2D for this population. Given the substantial and growing limited English proficient Chinese American population in the United States and the continued rising prevalence of T2D, there is an urgent need to develop, culturally-adapt, and test evidence-based interventions for diabetes control in this population.

While the majority of current diabetes interventions only involved patients, there is a growing body of evidence demonstrating the importance of educating and empowering family members in this process. The success of diabetes management depends largely on the social and environment contexts in which patients live and perform diabetes self-care. When patients with T2D live in a supportive family context (e.g., the family embraces a lifestyle consistent with the needs of the patient), they are more likely to receive social and emotional support for self-

management, adhere to diabetes self-care requirements, and achieve better glycemic control. Patients with T2D living in non-supportive family environments (e.g., family members undermine the patient's efforts, use negative communication strategies) have more difficulty initiating and sustaining recommended diabetes self-care behaviors, experience more diabetes-related distress, and report lower self-efficacy for self-management success. Disruptive family behaviors have been reported as major barriers to diabetes self-care in our recently completed mixed method study of 101 Chinese Americans with T2D.

Family interventions involving both patients with T2D and family members may be particularly useful for Chinese Americans given that the Asian culture places a strong emphasis on family ties. When one family member is affected by a disease, the other family members are often willing to provide help and support. Family members are well-positioned to provide the long-term support that sustains beyond an intervention study. Yet, family members often feel frustrated because they wanted to be involved in their loved ones' diabetes care but lacked knowledge and skills necessary to be more supportive or helpful. Despite the significant role of family members in diabetes self-management success, most interventions reported in the literature failed to include family members.

Mobile health (mHealth) such as using short message services (SMS) is a promising and practical strategy to deliver such a family intervention. A SMS-based family intervention is particularly relevant to Chinese Americans given that they often report long working hours and various challenges to attending in-person intervention sessions, which can be avoided using an mHealth approach. In addition, Chinese Americans are quite familiar with the SMS because of their social needs to connect with family and friends in the US and China. A SMS-based intervention has several advantages for educating and engaging patients in self-management and enhancing self-management support of their family members. In our recently completed mixed method study of 101 Chinese American patients with T2D, the idea of a SMS-based intervention was endorsed by the majority of participants. Participants also reported that their family members would be interested in receiving such an intervention. The efficacy of a family-based mHealth intervention involving both T2D patients and family members remains untested in Chinese Americans. To address this significant knowledge gap, the proposed study will leverage our current K99/R00 project, which aims to examine the potential efficacy of a patient-focused SMS intervention in Chinese Americans with T2D. This proposed study will adapt our K99/R00 **patient-focused** SMS intervention to a **family-oriented** SMS intervention, and pilot test it in a cohort of 30 Chinese American families (30 T2D patients and 30 their corresponding family members). Similar to the approach in our K99/R00 project, the culturally and linguistically adapted **family-oriented intervention will be delivered to participants via brief counseling videos sent to participants via SMS links (hereafter SMS intervention)**. Specifically, our aims are as follows:

## 2.2 Aims

**Primary Aim 1:** Assess the feasibility and acceptability of the SMS intervention in Chinese Americans with T2D and their family members

**Primary Aim 2:** Establish proof-of-concept regarding the potential efficacy of the SMS intervention for improving glycemic control

**Exploratory Aim:** Explore mediators of the SMS intervention

### 3. METHODS AND PROCEDURES

#### 3.1 Study Design

The proposed study is a pilot randomized controlled trial (RCT) of 6 months duration, with measurements at baseline, 3, and 6 months. Participants will be randomized to one of 2 arms (n=15 pairs each): 1) wait-list control; or 2) SMS intervention.

#### 3.2 Sites

The study will be conducted at the Charles B. Wang Community Health Center (CBWCHC), a federally qualified health center located in both Manhattan Chinatown and Queens Flushing Chinatown. In 2015, it provided a total of 275,749 service visits to 50,008 underserved Asian Americans in Greater NYC. The majority of patients are Chinese. CBWCHC is one of the largest and leading community centers in NYC, having established a trusting relationship with the Chinese American community. In 2016, approximately 5,000 patients with T2D were seen at the CBWCHC; the vast majority of them are Chinese. CBWCHC will not be engaged in research activities and their role is to identify/refer patients and provide space for this study. All research related activities (e.g. recruitment, consenting, conducting study procedures) will be performed by NYU study staff. The letter of support has been uploaded in the attachment section.

To maximize recruitment efforts, we will also identify potential private practices or community based organizations in Chinatown areas and work with them to recruit potential participants. In addition, we will identify and recruit participants into the study from NYU Langone Health. **Similar to the procedures at CBWCHC, all of the research related activities (e.g. recruitment, consenting, conducting study procedures) will be performed by NYU study staff. The role of these private practices, NYU Langone Health, or community based organizations is to help to identify/refer patients and/or provide space for this study.**

#### 3.3. Characteristics of the Research Population

We will recruit **60 participants for this project**, including 30 T2D Chinese patients and 30 corresponding family members. Family member is broadly defined as any support person who the patient considers plays a vital role in their diabetes self-management and would be interested in receiving such interventions. This can be spouse, adult children, siblings, or friends.

**Inclusion criteria for patient participants:** To be eligible for the study, patient participants must: 1) self-identify as Chinese immigrant or Chinese American; 2) be between the ages of 18 and 70; 3) be able to speak and understand Mandarin; 4) self-report a diagnosis of T2D; 5) baseline HbA1c  $\geq 7\%$ ; 6) be currently using WeChat; 7) be willing to receive WeChat or text messages regarding T2D management; 8) express strong interest and confidence in finishing watching 2 diabetes videos each week for a total of 12 weeks; 9) be motivated to make lifestyle changes to control their diabetes; and 10) have a family member or friend be willing to participate in the study to learn about T2D to better support them.

**Inclusion criteria for family/friend participants:** Family/friend participants must 1) self-identify as Chinese immigrant or Chinese American; 2) be between 18-70 years old; 3) be able to speak and understand Mandarin; 4) be currently using WeChat or text messages; 5) be willing to receive WeChat or text messages regarding T2D management and learn how to better support the patient with T2D; 6) express strong interest and confidence in finishing watching 2 diabetes videos each week for a total of 12 weeks; and 7) be motivated to support their family/friend to make lifestyle changes to control their diabetes.

**Exclusion criteria for both patient and family/friend participants:** Individuals will be excluded from participation if they meet any of the following: (1) unable or unwilling to provide verbal consent; (2) unable to participate meaningfully in the intervention (e.g., uncorrected sight and hearing impairment); (3) unwilling to accept randomization assignment; (4) pregnant, plans to become pregnant in the next 6 months, or who become pregnant during the study, (5) breastfeeding, or (6) live in a facility or other health care setting where they have no control over diabetes self-management.

## 4. PROCEDURES

### 4.1 Patient Recruitment

Participants be identified and recruited into the study from NYC health care facilities, including CBWCHC, private practices, and NYU Langone Brooklyn and affiliated provider practices.

We will recruit participants using the following methods:

**a. Posters.** Posters will be placed in NYC health care facilities waiting and examination rooms. Posters will list a contact telephone number that patients can call if interested in enrolling. Patients who self-refer will be screened for eligibility. Posters will also be placed in Chinese community centers (e.g., senior centers) and distributed during Chinese community events. Posters will also be posted electronically on WeChat, which is a very popular chatting smartphone application among Chinese Americans and Chinese Immigrants.

**b. Direct referral by NYC health care providers.** CBWCHC, NYU Langone Brooklyn site providers, and private practice health care providers will approach patients who are potentially eligible for the study, solicit their interest in the study. If patients express verbal interest in the study participation, their health care providers will share the patient's contact information to the study staff, or patients will also be able to call (self-refer to) to the number provided in the recruitment flyer and speak with a study staff if they are interested in participating. Study staff will call the patient and screen for eligibility. Meanwhile, patients will be invited to call (self-refer to) the study staff if they are interested in participating. Study staff will call the patient and with the patient's verbal consent the staff will conduct a quick phone pre-screening to confirm eligibility prior to enrollment. [name] is the medical director at NYU Brooklyn Family Health Center. We are collaborating with [name] and her team at NYU Brooklyn. They would help refer potential study participants that are eligible and interested in our study. The initial referral list from health care providers will only include patient's name and phone number for those verbally expressed interest in the study. After verbal consent is obtained and documented, the study staff will request the patient's medical information from the medical record.

**c. Registry lists.** From our previous study, we have created a registry list of potential participants who indicated interest in future studies from NYU School of Medicine. We will call participants from the registry list, explain the study, and assess the eligibility to participate.

**d. EPIC and DataCore.** We will work with DataCore to generate a report to identify potentially eligible subjects across NYU Langone Manhattan, Brooklyn, and Long Island campuses. Using a query, search will be conducted in EPIC to identify Chinese patients aged 18-70 and with type 2 diabetes whose most recent HbA1c value  $\geq 7\%$ . The report will also include demographics including patient name, gender/sex, date of birth, address, phone number, weight, height, BMI, name of primary care physician, most recent HbA1c value and date of measurement. Only the principal investigator and all members of the research team will have access to this report. The report will be generated prior to the recruitment process to help us find potential participants. The report will be kept on a secure electronic drive to ensure the

confidentiality of health information and identifying information from potential participants. These patients will receive a mailing describing the study and letting them know how they can opt out of further contact. The study staff will call patients who have not opted out to describe the study, complete the brief eligibility screener and offer enrollment. While screening potential participants by telephone, demographics and the most recent HbA1c value will be confirmed or updated.

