## 5. RISK/BENEFIT ASSESSMENT

### 5.1 *Potential Risks*

Risks of participation in this study are minimal and unlikely to occur given the safeguards in place. Psychological risks include: 1) the possibility that some participants may perceive some questionnaire or background data assessment as intrusive or causing them to feel uncomfortable; 2) breach of confidentiality. For the confidentiality protection related to audio-recording, we will store all the recordings on a password protected server. We will use a unique code number during the transcription. Once the transcription is done, all the audio recordings will be destroyed.

There is a potential risk for breach of confidentiality on WeChat. To minimize the risk, we will remind participants that they should call our study phone number for any questions related to the study participation. WeChat will only be used to send education videos. No communication will occur via WeChat. Also, we will remind them at the beginning of the study and during the bi-weekly phone calls about not sending any Protected Health Information via WeChat. In addition, our education videos do not contain any Protected Health Information and it will teach participants about diet, exercise, and stress management in general. Based on our recent completed pilot study (a similar WeChat video study in 30 Chinese immigrants), we did not observe any breach of privacy or confidentiality. All of the study team members received sufficient training on protecting privacy and confidentiality and have extensive experience in working with this hard-to-reach immigrant population. The benefits of receiving these culturally and linguistically tailored education videos outweighed the risks.

The study involves an intervention designed to enhance adherence to standard diabetes care (e.g., adherence to the prescribed diabetes medication, healthy eating, and physical activity behaviors). If our intervention improves adherence to the medication regimen or if participants make lifestyle changes (e.g., increased physical activity), more episodes of hypoglycemia may result. We will advise participants of the importance of monitoring their blood sugar as suggested by their doctors, and to contact their doctors as soon as they experience low blood sugar.

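### Nothing in eligibility or screening keeps out people who have had, or are having, the team's related SMS/WeChat diabetes videos, so the HbA1c contrast may be diluted to an unknown extent

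*Combined protocol and SAP*

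**What the plan says.** Section 4.1 lists four recruitment routes: posters, provider referral, a registry and an EPIC/DataCore query. On the registry it says "From our previous study, we have created a registry list of potential participants who indicated interest in future studies". Staff call these people and assess eligibility. The source study is not identified.

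Section 2.1 says that this trial "will leverage our current K99/R00 project, which aims to examine the potential efficacy of a patient-focused SMS intervention in Chinese Americans with T2D". The family-oriented intervention is an adaptation of that patient-focused one, and its delivery by video link is described as "Similar to the approach in our K99/R00 project". Section 5.1 mentions a recently completed pilot, "a similar WeChat video study in 30 Chinese immigrants".

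Section 3.3 gives ten inclusion criteria for patients and seven for family or friends. It then gives six exclusions for both, introduced by "Individuals will be excluded from participation if they meet any of the following". These cover consent, ability to take part, acceptance of randomization, pregnancy, breastfeeding and residence in a facility.

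Under Section 4.3, wait-list controls have usual care and are offered the videos only once the study ends.

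**The concern.** The control arm is defined by the absence of the videos, yet the rules as written admit someone who has already watched the parent material or is enrolled in a project that delivers it. The inclusion items on willingness to receive messages and confidence in finishing the videos would, if anything, suit such people.

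Two results are at stake. One is the HbA1c comparison for Primary Aim 2, because Section 7.1 plans to take the effect size from this pilot to size the R01 trial. The other is the primary feasibility outcome, the percentage of sent videos that are watched. A previously exposed person may watch more, having shown willingness, or less, because the content is familiar. The figure may then be a poor guide to naive patients.

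**Working it through.** **1. Is exposure handled anywhere?** The relevant places, taken in turn:

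- Section 3.3: 10 patient inclusion items, 7 family/friend inclusion items and 6 exclusions. None concerns earlier or concurrent receipt of the videos, or enrolment in another study.
- Sections 4.1 to 4.3, recruitment, consent and procedures: a phone screener is described, with no exposure question mentioned.
- Section 4.3, covariates: sociodemographic, health and survey items. Earlier exposure to a video programme is not listed.
- Section 7.1, analysis: no adjustment or sensitivity analysis for exposure.

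So exposure is neither excluded, screened for, recorded nor adjusted for.

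**2. How could exposure act?** The timing matters.

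- *During follow-up, in a control:* the control receives something close to the intervention while HbA1c is being compared. This reduces the contrast directly.
- *Before enrolment:* any effect already achieved is in the baseline HbA1c and is balanced between arms in expectation. The remaining route is that an exposed SMS-arm patient may gain less from seeing similar material again.

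Both routes move the contrast toward zero. At 15 per arm there may also be chance imbalance, but no systematic shift toward one arm.

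**3. Scale, for illustration only.** The plan gives no effect size, SD or power calculation for the pilot, so there is no stated figure to reproduce. Inputs: 15 patients per arm (Section 3.1); two-sided alpha 0.05 and power 0.80 for the future trial (Section 7.1). Everything else below is assumed.

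Let D be the true contrast in naive patients and k the number of controls who obtain the full effect during follow-up, with the SMS arm naive:

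expected contrast = D × (1 − k/15)

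The required sample size varies as 1/(effect size)², so the multiplier on the future trial is 1/(1 − k/15)².

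| k | Loss of contrast | Multiplier on future n |
|---|---|---|
| 1 | 1/15 = 6.7% | 1.15 |
| 2 | 2/15 = 13.3% | 1.33 |
| 3 | 3/15 = 20% | 1.56 |

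For earlier exposure, let m SMS-arm patients each lose a share c of the effect. The expected contrast is then D × (1 − m × c/15). For example, m = 2 and c = 0.5 gives 1/15, again 6.7%.

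As a worked case, assume a true standardised effect of 0.5. The future trial needs 2 × (1.960 + 0.842)²/0.5² = 62.8, so 63 per arm. With a 20% loss the expected effect is 0.40 and the same formula gives 98.1, so 99 per arm.

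**4. Can k, m or c be estimated from the documents?** No. They do not name the registry's source, do not say whether the K99/R00 project and the completed pilot are one study, and give no number of exposed people who might enrol.

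**The case against.** The strongest reply is that exposure is inferred. Section 2.1 also describes another candidate source for the registry: "In our recently completed mixed method study of 101 Chinese American patients with T2D". No videos are described in that study, and it is at least as plausible an origin as a video study. A reader might infer that registry members have seen the videos; the documents do not say so. This stands. The gap does not depend on the registry, however, because the other three routes carry no exposure check either.

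A reader might also infer that the K99/R00 project delivers videos alongside this trial, and add its participants to those of the pilot. Section 2.1 calls the project current and Section 5.1 calls the pilot completed. Whether these are two studies, and whether delivery overlaps with this trial's follow-up, is not stated. Adding them could count the same people twice.

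It is also tempting to call any previously exposed control a treated control. That is wrong for this comparison, for the reason in step 2 of the working.

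Nor is it reasonable to assume that exposed patients gain nothing further. They must still have HbA1c of at least 7% to enrol, a family member is newly involved, and there are family-oriented sessions, goal setting and biweekly calls.

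Finally, dilution is small beside pilot noise. The standard error of a standardised difference with 15 per arm is about √(2/15) = 0.37, so the 95% half-width is about 0.7. One exposed control at an assumed effect of 0.5 moves the expected value by 0.5/15 = 0.03. This is fair. It limits the weight of the point but does not remove it, because dilution is a downward shift in the expected value carried into the R01 sizing, and it is cheap to prevent.

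**Conclusion.** The point holds as a gap in who may be randomised. The plan admits patients and family members exposed to closely related videos and has no means of knowing it. The consequences are possible dilution of the HbA1c contrast and uncertain representativeness of the viewing rate.

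The size is unknown. The figure of about 6.7% per fully exposed control assumes that the control obtains the whole effect during follow-up and that the SMS arm is naive. It is a scale, not an estimate. A reader might go on to claim an overall attenuation of 10% or 30%. That would need a number of exposed participants that the documents do not give, plus the extreme assumption of no further gain. The 30 people in the completed pilot do not supply that number. A claim of bias favouring either arm is likewise unsupported.

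The change is worth making because it is specific, inexpensive and must precede enrolment.

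**What to change.** - Add to the exclusions in Section 3.3, for patients and for family/friends: has received the team's SMS/WeChat diabetes videos, or is enrolled in a study that may deliver them during the 6-month follow-up.
- Apply it by a question in the phone screener.
- Name the registry's source study in Section 4.1, and state whether the K99/R00 project and the completed pilot are the same study.
- Ask controls at the 3- and 6-month visits whether they saw any such videos, and report the count.
- If the team prefers to keep previously exposed people, record exposure at baseline and report viewing and HbA1c with and without them.

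The cost is one criterion, one screening question, one follow-up item for controls and a somewhat smaller pool. The loss cannot be sized from the documents. The roughly 5,000 patients with T2D seen at the community health center in 2016 (Section 3.2) are not all eligible, since HbA1c, language, WeChat use and a willing partner all narrow that number. According to Section 3.2, NYU study staff carry out all recruitment and consent, so the question adds little work.
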